Protocol: A usability assessment of intramuscular, atomized intranasal, and nasal spray administration of naloxone by untrained community members

Primary Investigator: [name]

Background: Opioid abuse and addiction is a growing epidemic both in the United States and globally. It impacts the health, social welfare, and economic stability of those directly affected and society as a whole. According to the National Institute on Drug Abuse there are approximately 2.1 million people in the United States with substance use disorders related to prescription opioid medications and another 467,000 addicted to heroin. Data from the Center for Disease Control National Vital Statistics System demonstrated that the number of drug poisonings involving opioid analgesics tripled from 2000 to 2014, and in 2010 opioid pain relievers were responsible for 82.8% of all unintentional deaths in the United States.¹ In an attempt to combat this epidemic many states have implemented community-based opioid overdose prevention programs aimed at increasing resources to combat addiction and distributing naloxone to community members. These programs increase knowledge of overdose prevention and the factors that increase a person's risk for overdose. Evaluations of these programs have also demonstrated that nonmedical bystanders are able to administer naloxone effectively after completing training.² Naloxone can be administered intravenously, intramuscularly, or via inhalation. Opioid overdose prevention programs are typically initiated by local and state governments, which allows for interprogram variability regarding the route of naloxone administration used by community members. Pre-hospital data has demonstrated that intranasal naloxone is a safe and effective alternative to intravenous naloxone.³ A usability assessment comparing a naloxone auto-injector (Evzio®) to the use of a nasal atomizer suggested that the route of administration did impact the rate of successful naloxone administration by nonmedical community members.⁴ Opioid overdose prevention programs typically utilize intranasal atomizers, nasal inhalers, or intramuscular administration routes. In 2016 we conducted a usability assessment of naloxone administered by community members who received training on how to use the naloxone device they were assigned. Our data supported that intranasal administration with an atomizer or spray resulted in a higher administration success rate when compared to intramuscular injection. Recently, New York, along with many other states, passed legislation allowing individuals to purchase naloxone over-the-counter without a prescription. This legislation has drastically expanded access to naloxone, but has reduced the opportunity to train community members purchasing the medication. We plan to conduct a usability assessment of simulated naloxone in community members in the absence of training to assess the rate of successful administration and time to successful administration.

Objectives:

Primary: The successful administration of simulated naloxone without training. A successful administration will be defined as administration of the simulated naloxone to the mannequin head or simulated flesh pad within 7 minutes and without any critical errors (defined below).

Secondary:

-Total time required to successfully administer the simulated naloxone without training.

- Comparison of successful administration with standard and simplified instructions
- Comparison of total time required for successful administration with standard and simplified instructions
- Likert-item assessment of the usability of the simulated naloxone product
- Likert-item assessment of usability of the naloxone administration instructions

Design: Single site, open-label, randomized usability assessment of intramuscular, intranasal, and nasal spray administration of simulated naloxone using standard (package-insert) or simplified (developed by study team) instructions. A convenience sample of participants will consent to volunteer in the study at a public venue. Participants will provide verbal consent and will be randomly assigned a simulated naloxone kit containing either intramuscular standard, intramuscular simplified, intranasal standard, intranasal simplified, nasal spray standard, or nasal spray simplified administration materials. The participant will enter a use scenario station where they will be asked to assemble and administer the simulated naloxone kit to a mannequin (intranasal and nasal spray) or simulated flesh pad (intramuscular). The participant will be instructed to start and will be timed until the simulated naloxone has been successfully administered or 7 minutes has elapsed. The participant will be observed by one trained investigator who will assess for successful administration of the simulated naloxone and critical errors. The environment will contain distracters to mimic a community based setting. Once the participant has successfully administered the simulated naloxone or 7 minutes has elapsed the timer will be stopped. Successful administration of simulated naloxone will be defined as administration of the agent without any critical errors occurring (defined below). Data collected will include demographics (defined below), successful administration of simulated naloxone, product assessment information, instruction assessment information, and time to successful administration of simulated naloxone.

Eligibility: healthy adults (18 years of age and older) at a public venue will be asked to participate in the study. Participants will be excluded if they are severely visually or hearing impaired (defined as: legally deaf, legally blind, unable to read print size provided on instructional handout, or unable to hear instructions from a research staff member), have previous naloxone administration training, are not English proficient, state that they may be pregnant, or they have previously participated in the trial.

Statistical Methods: All data will be analyzed using IBM SPSS Statistics software. Demographics data will be analyzed using descriptive statistics for continuous measures and percentages for categorical measures. The successful administration of naloxone will be compared between groups using the Chi-square test and a significant difference will be defined as a p-value of less than 0.05 for the result. The time to administration between groups will be assessed using a one-way ANOVA and a significant difference will be defined as a p-value of less than 0.05 for the result. The Likert-item data will be reported as percentage of response level and analyzed using a one-way ANOVA with a significant difference defined as a p-value of less than 0.05 for comparison between administration methods and instruction methods.

Data Analysis/Interpretation: As stated above data will be collected to assess both the successful administration of and time to administration of naloxone. The rate of successful administration will be

reported as a percentage for each of the three groups and analyzed using the Chi-square test. Successful administration is defined as administration of the simulated naloxone within 7 minutes without committing any critical errors. Critical errors are as follows:

[figure not shown]
- Intranasal (atomizer): failure to remove both yellow caps from bristoject, failure to remove cap from simulated naloxone, failure to attach atomizer, failure to attach simulated naloxone, drug leak prior to administration, administration in only one nostril, and failure to administer within 7 minutes.
- Intramuscular: failure to attach the needle to the syringe, failure to remove cap from simulated naloxone, failure to draw up >90% (0.9 mL) of the simulated naloxone, failure to puncture simulated flesh pad with needle, failure to push entire volume of fluid in the syringe into the simulated flesh pad, and failure to administer within 7 minutes.
- Intranasal (spray): failure to place the tip of the device into one nostril, failure to depress the device and release the simulated naloxone, failure to administer within 7 minutes.

Time to successful administration will be reported using descriptive statistics (mean time to administration) and analyzed using a one-way ANOVA. Times for participants who commit a critical error or who do not administer the simulated naloxone within 7 minutes will not be included in the analysis. The Likert-item data will be reported as a median with an inter-quartile range and analyzed using a one-way ANOVA.

A route of administration will be considered to be more user-friendly if it demonstrates a statistically significantly higher rate of successful administration compared to another route of administration. Additionally, a route or instruction type will be considered user preferred if the Likert-item data demonstrates a significantly better score on usability.

Study Procedures: No study procedures will be performed on study participants.

Diagram of Study Design:

Investigators observe the administration and record if the administration is successful, the time to administration, and the critical error that occurred if applicable. Survey data is

Works Cited

1. Volkow ND. America's Addiction to Opioids: Heroin and Prescription Drug Abuse. <https://www.drugabuse.gov/about-nida/legislative-activities/testimony-to-congress/2016/americas-addiction-to-opioids-heroin-prescription-drug-abuse>. Published May 14, 2014. Accessed June 24, 2016.

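### Asking every participant to assemble the kit could cue a step that is scored as a critical error for the atomizer and intramuscular routes but not for the spray

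*Combined protocol and SAP*

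**What the plan says.** The primary objective is "The successful administration of simulated naloxone without training", scored as a success only if the attempt is completed within 7 minutes with no critical error.

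The Design section describes six randomised kits, three routes by two instruction types, "using standard (package-insert) or simplified (developed by study team) instructions". One sentence then sets the task for all of them: "they will be asked to assemble and administer the simulated naloxone kit to a mannequin", with the flesh pad as the intramuscular target.

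The critical errors are listed by route under Data Analysis/Interpretation:

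- The atomizer list includes "failure to attach atomizer, failure to attach simulated naloxone".
- The intramuscular list includes "failure to attach the needle to the syringe".
- The spray list consists of "failure to place the tip of the device into one nostril, failure to depress the device and release the simulated naloxone", plus the 7-minute limit.

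A route is to be called more user-friendly when its success rate is significantly higher than another's.

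**The concern.** The trial asks what an untrained person does with a kit and its written instructions. For two of the routes, part of what is scored is whether the person joins the parts at all. A task statement that mentions assembly tells the participant, before the clock starts, that something has to be put together. On the spray the same word points to no scored step.

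One critical error fails the whole attempt, so preventing a single omission can change the primary outcome. Three things are at stake:

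- the success rate reported for the atomizer and intramuscular kits as an estimate of untrained use;
- the comparison of those routes with the spray, which decides the user-friendliness verdict;
- the comparison of standard with simplified instructions, because both arms would receive by ear something the paper is supposed to convey.

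Every participant would receive the same prompt and there is no unprompted group, so any such effect could not be estimated or removed in the analysis.

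**Working it through.** **1. Count the scored assembly steps.** The inputs are the three critical-error lists under Data Analysis/Interpretation.

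| Route | Items listed | Attachment items | Attachment plus other preparation (caps, drawing up) |
|---|---|---|---|
| Atomizer | 7 | 2 | 4 |
| Intramuscular | 6 | 1 | 3 |
| Spray | 3 | 0 | 0 |

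The asymmetry is present on either reading. The attachment count is the fairer one, since the word says nothing about caps or volumes.

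**2. Look for a figure to reproduce.** There is none. The document gives no expected success rate, sample size or power, and no rate at which assembly steps fail. Everything below is therefore assumption, shown as a range.

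**3. Possible rise in the success rate.** For a kit that needs assembly, let

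- *a* = probability of an assembly failure without the cue,
- *b* = probability of any other critical error, taken as independent of *a*,
- *f* = share of assembly failures that the cue prevents.

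Success without the cue is (1 − a)(1 − b). With the cue it is (1 − a(1 − f))(1 − b). The rise is the difference, a × f × (1 − b). For example, with a = 0.20, b = 0.20 and f = 0.25, success goes from 0.80 × 0.80 = 0.64 to 0.85 × 0.80 = 0.68, a rise of 4 points.

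Rise in percentage points:

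| b | a | f = 0 | f = 0.25 | f = 0.5 | f = 1 |
|---|---|---|---|---|---|
| 0.2 | 0.05 | 0 | 1.0 | 2.0 | 4.0 |
| 0.2 | 0.10 | 0 | 2.0 | 4.0 | 8.0 |
| 0.2 | 0.20 | 0 | 4.0 | 8.0 | 16.0 |
| 0.2 | 0.30 | 0 | 6.0 | 12.0 | 24.0 |
| 0.4 | 0.05 | 0 | 0.8 | 1.5 | 3.0 |
| 0.4 | 0.10 | 0 | 1.5 | 3.0 | 6.0 |
| 0.4 | 0.20 | 0 | 3.0 | 6.0 | 12.0 |
| 0.4 | 0.30 | 0 | 4.5 | 9.0 | 18.0 |

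The column f = 0 is the case where the written instructions already convey everything the word does. The column f = 1, where the cue prevents every assembly failure, is an upper bound and not a plausible value.

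**4. Illustration for one pair of routes.** Assume 95% success on the spray and 80% uncued success on a kit that needs assembly, and let the cue rescue 0, 2.5, 5 or 10 points. Power is by the normal approximation for two proportions, two-sided 5%.

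| Rescued points | Gap (points) | Power, 100 per route | Power, 50 per route |
|---|---|---|---|
| 0 | 15 | 0.90 | 0.62 |
| 2.5 | 12.5 | 0.80 | 0.51 |
| 5 | 10 | 0.66 | 0.38 |
| 10 | 5 | 0.27 | 0.16 |

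The result depends heavily on the baseline. With 95% against 60%, rescuing 10 points moves power at 50 per route only from 0.99 to 0.92, and at 100 per route it stays at about 1.0. The 10-point row of the table is also extreme: from 80% success, it means the cue saves 10 of the 20 failing points, or half of all failures. These figures show how the mechanism would work. They are not evidence that it does.

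**The case against.** The strongest reply has four parts.

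- **The sentence may not be the script.** It describes the task for all three routes at once, and no verbatim wording is given. This stands. The Eligibility section excludes people who cannot hear staff instructions, so something is said, but not necessarily this. If the sentence is only a summary, what remains is that the available text fixes no neutral wording and nothing stops staff from using this one.
- **Every participant has written instructions.** Untrained does not mean uninstructed. If the materials explain assembly, which cannot be checked because they are not reproduced, one generic word may add little or nothing. This stands, and it is why zero belongs in the range. It does not remove the concern, since whether people read and follow the paper is part of what is tested.
- **The cue is thin.** It does not say which parts to join or how. It does not touch leaks, single-nostril use, volume drawn up, puncture or full delivery. A rescued participant must still avoid all of these. This stands and limits the size.
- **Dilution of the instruction contrast is conditional.** It arises only if the two sets of materials differ in how well they convey that assembly is needed. This too stands.

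A reader might go further and infer that untrained success *is* inflated for two routes, or that the trial loses a stated amount of power. The document supports neither. It has no figure for assembly failures or for the effect of the wording, and the power figures follow wholly from chosen inputs.

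**Conclusion.** The concern holds as a possible, route-dependent cue of unknown size. The text establishes two things: the stated task names assembly, and attaching parts is scored on two routes and not on the third. The effect is conditional on staff using the wording and on it adding something to the written instructions. If both are true, it would raise measured success for the atomizer and intramuscular kits. It would narrow their gap to the spray where the spray is ahead.

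Under the assumed values (a from 5% to 30%, b of 20% or 40%), the rise is 0 points if f = 0, 0.8 to 6 points if f = 0.25, and 1.5 to 12 points if f = 0.5. The document does not favour any of these over the others. One figure and the study diagram could not be read in the text available, so any task wording there was not checked.

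This is a cheap improvement to make before enrolment. It is not a demonstrated bias.

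**What to change.** In the Design section, delete *assemble and* from the sentence that sets the task. Add that staff will read one neutral task statement, word for word and identical in all six arms, that names no step on any critical-error list. For example: *use this kit on the model in front of you*.

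The cost is one sentence of protocol text and a script card, with no extra participants, staff or procedures. The downside is that observed success for the kits that need assembly may be slightly lower.

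### People who have watched another participant's attempt remain eligible and, if the station can be seen, would be counted in the untrained success rate

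*Combined protocol and SAP*

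**What the plan says.** The primary objective is "The successful administration of simulated naloxone without training". Under Data Analysis/Interpretation, the success rate is reported as a percentage for each of the three routes.

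On recruitment, the Design section states: "A convenience sample of participants will consent to volunteer in the study at a public venue". On the attempt itself: "The participant will enter a use scenario station where they will be asked to assemble and administer the simulated naloxone kit". It adds: "The environment will contain distracters to mimic a community based setting". One trained investigator observes, and an attempt may last up to 7 minutes.

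Two exclusions in Eligibility deal with prior exposure. One covers people who "have previous naloxone administration training, are not English proficient" (the first clause is the relevant one). The other closes the list: "state that they may be pregnant, or they have previously participated in the trial". Training is not defined. Having seen another person's attempt is not mentioned in Eligibility, and the data items listed in the Design section do not include it.

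**The concern.** By barring trained people and repeat participants, the plan already accepts that prior exposure spoils the measurement. Watching someone assemble and use a kit a few minutes earlier is exposure of a similar kind, yet it is not excluded, asked about or recorded. At a public venue, with attempts of up to 7 minutes, it is plausible that later volunteers are nearby.

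What is at stake is mainly the absolute success percentage for each route. The Background motivates the study by over-the-counter purchase without training, so that percentage is the figure readers will carry away. Randomisation does not protect it, because watchers would be present in every arm. Times to success could be affected in the same way. If viewing is not recorded, no later analysis can separate the watchers from the rest.

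**Working it through.** The document gives no sample size, expected success rate or effect size, so there is no planned figure to reproduce. The check has a reading part and an illustrative part.

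**1. Reading for any safeguard.**

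| Possible safeguard | Where it would stand | Found? |
|---|---|---|
| Exclusion for having watched an attempt | Eligibility | No; only prior training and prior participation |
| Screening question on prior viewing | Eligibility | No |
| Station out of sight, or waiting volunteers kept apart | Design | No; participants enter a station, layout not described |
| Prior viewing recorded as data | Design, data items | No |

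**2. Bias in an absolute rate.** Let p be the success rate of people who have not watched, q the rate of those who have, and w the share who have watched. The reported rate is p + w(q − p), so the bias is w(q − p).

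Assumed ranges, not from the document: w = 10% to 30% and q − p = 10 to 30 percentage points.

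- Lowest: 0.10 × 0.10 = 0.01, or 1 point.
- Highest: 0.30 × 0.30 = 0.09, or 9 points.

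This gives every watcher the full gain.

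**3. Allowing for kit mismatch.** Participants are randomised among six kits, three routes by two instruction types. The allocation ratio is not stated. If it is equal, a single watched attempt has the same route as the kit later assigned with probability 1/3. If the gain carries over only then:

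- Lowest: 0.01 × 1/3 = 0.0033, or about 0.3 point.
- Highest: 0.09 × 1/3 = 0.03, or 3 points.

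Someone who watched several attempts would be more likely to have seen the assigned route. The whole range is therefore roughly 0.3 to 9 points. A true untrained rate of 50%, for example, would be reported as 50.3% to 59%.

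**4. Direction.** Upward is the likelier direction, but it is not certain. For the spray, the critical-error list requires the tip to go into one nostril. For the atomizer, giving the dose in only one nostril is itself a critical error. Someone who watched a spray attempt and then drew the atomizer could be led into that error. Watching a failed attempt could also mislead.

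**5. Route contrast.** Leaving aside the time limit, the plan lists six critical errors for the atomizer, five for intramuscular and two for the spray, so there is more to learn by watching the multi-step kits. As an illustration on assumed rates, suppose watching raises a harder route from 60% to 80% and an easier one from 80% to 90%. The observed difference is then (0.80 + 0.10w) − (0.60 + 0.20w) = 0.20 − 0.10w. Sample sizes are for a two-sided 0.05 test of two proportions with 80% power.

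| w | Difference (points) | n per group |
|---|---|---|
| 0 | 20 | 82 |
| 10% | 19 | 88 |
| 20% | 18 | 95 |
| 30% | 17 | 103 |

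This illustration also gives every watcher the full gain, so mismatch would make the dilution smaller. The misdirection in step 4 could instead widen the contrast between spray and atomizer.

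**The case against.** The strongest reply is that the premise cannot be seen in the text. Nothing says that people queue, come in groups or can look into the station. Entering a station fits an enclosed space as well as an open one. The study diagram, which might show the layout, is missing from the text available for this review. This stands, and it makes the size of the problem conditional on a layout that only the sponsor knows. It does not close the gap in the eligibility rule, and enclosure alone would not stop a volunteer being told what to do.

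Staff might also screen out someone who had been told how to use the kit, by reading the prior-training exclusion broadly. That is reasonable, but the wording does not require it, and passive watching is still uncovered.

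The comparisons are largely protected, and this stands too. Kits are assigned individually, so watchers are balanced across arms in expectation and no false difference arises from an imbalance of watchers. The rule for calling a route more user-friendly rests on between-route significance, not on the absolute rate.

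Two stronger readings are tempting. A reader might infer that volunteers are in effect coached; the document offers no support for that. A reader might also infer that companions enrolled together break the independence assumed by the chi-square test and ANOVA. The document does not say that people enrol in groups. Even if they did, with individual assignment, positive correlation among companions spread over the arms does not generally inflate false positives between arms. There is no case here for limiting enrolment to one person per group.

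**Conclusion.** The gap is real and its scope is limited. As written, a person who has watched another attempt is eligible and would be analysed as untrained, and nothing would show it afterwards. If the station is visible, the absolute success rates and times could be biased, most likely upward. For the rates, the size is roughly 0.3 to 9 points. That rests on assumed shares of 10–30% and assumed gains of 10–30 points; the low end also assumes equal allocation, one watched attempt and a gain confined to a matching route.

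Route and instruction contrasts may be somewhat altered or diluted. A reader might go further and infer that the untrained rates are known to be too high, or that the significance tests are unsound. The document supports neither: visibility is not stated, the direction can reverse, and random assignment keeps the tests valid as comparisons of the kits in the people recruited. This is a cheap improvement that should be made before enrolment.

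**What to change.** 1. Add one exclusion to Eligibility: *has watched, or been told how to carry out, another participant's attempt in this study*.
2. Ask it as a single screening question before randomisation.
3. State in the Design section that the station is out of sight of waiting volunteers. If it is already enclosed, one sentence saying so is enough, and the screening question is still needed.

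At minimum, if the sponsor prefers not to exclude anyone, record prior viewing as a data item before randomisation and repeat the primary analysis without those participants.

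The cost is one eligibility line, one question, a screen or a suitable position for the station, and the loss of a few volunteers.

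### Time is compared by ordinary ANOVA among successes only: the comparison depends on a post-randomisation outcome, and its 5% level is not guaranteed if spread and group size both differ

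*Combined protocol and SAP*

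**What the plan says.** Time is a secondary objective: "Total time required to successfully administer the simulated naloxone without training". A further secondary objective compares time between the two instruction types. Under Design, each participant "will be timed until the simulated naloxone has been successfully administered or 7 minutes has elapsed".

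Statistical Methods: "The time to administration between groups will be assessed using a one-way ANOVA", where "a significant difference will be defined as a p-value of less than 0.05 for the result". Data Analysis/Interpretation repeats the test and names the summary: time is "reported using descriptive statistics (mean time to administration) and analyzed using a one-way ANOVA". It then restricts the data: "Times for participants who commit a critical error or who do not administer the simulated naloxone within 7 minutes will not be included".

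No assumption check, Welch correction, transformation, rank test or time-to-event method is planned for time. In ordinary usage an unqualified one-way ANOVA is the equal-variance F test; that is my reading, as the plan does not use the term. The documents give no sample size, SD, success rate or distribution of times.

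**The concern.** Two things follow from dropping failures.

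- **Selection.** Success is observed after randomisation and may depend on the kit assigned. The people who succeed with one kit need not be comparable with those who succeed with another. A kit that only quick, able users can operate could look fast because everyone else has been removed. No choice of ANOVA variant cures this.
- **Unequal group sizes.** The number of times in each group follows the success rate. The Background reports that, in the sponsor's earlier study of trained users, success was higher with both nasal routes than with intramuscular injection. Fewer intramuscular times would be a natural expectation here.

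The ordinary F test pools the within-group variances, weighted by group size. If a small group also has a wide spread, the pooled variance is too small for that group and the test rejects too often. If the small group has a narrow spread, the test rejects too rarely. At stake is whether a p-value below 0.05 for time means what the plan says it means.

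**Working it through.** The plan has no derived figure to reproduce; 0.05 is only a threshold. The check is therefore how the planned test behaves under stated assumptions.

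**From the documents:** one-way ANOVA of mean time, threshold 0.05, successes only, upper limit 7 minutes (420 s), and the direction of success rates by route.

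**Assumed:** right-skewed (lognormal) times truncated at 420 s; three groups with equal true means of 150 s; coefficients of variation (0.7, 0.5, 0.4), (0.8, 0.5, 0.3) or (0.6, 0.45, 0.35), giving SDs of about 77-88, 64-69 and 45-58 s; analysed sizes 20/30/47 or 25/60/95.

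**Step 1: why the level moves.** F = MSB / MSW. With equal means, N = Σnᵢ and k groups:

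- E[MSB] = Σ(1 − nᵢ/N)σᵢ² / (k − 1)
- E[MSW] = Σ(nᵢ − 1)σᵢ² / (N − k)

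Take SDs 88, 69 and 45 s (variances 7744, 4761, 2025).

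- Sizes 25/60/95, smallest group widest: MSB = (155/180 × 7744 + 120/180 × 4761 + 85/180 × 2025)/2 = 5399. MSW = (24 × 7744 + 59 × 4761 + 94 × 2025)/177 = 3712. Ratio 1.45, so F is too large.
- Sizes 95/60/25, smallest group narrowest: MSB = (85/180 × 7744 + 120/180 × 4761 + 155/180 × 2025)/2 = 4287. MSW = (94 × 7744 + 59 × 4761 + 24 × 2025)/177 = 5974. Ratio 0.72, so F is too small.
- Equal sizes: both equal (7744 + 4761 + 2025)/3 = 4843. Ratio 1.00.

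**Step 2: simulated type I error** (20,000 trials per case, simulation error about 0.2 points):

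| Case (equal true means) | Ordinary ANOVA | Welch, raw seconds |
|---|---|---|
| 20/30/47, smallest group widest | 7.6-10.6% | 5.6-6.1% across both |
| 25/60/95, smallest group widest | 8.9-13.3% | (as above) |
| Equal sizes | 5.1-5.5% | – |
| Sizes reversed (47/30/20, 95/60/25) | 2.2-3.3% | – |

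**Step 3: other assumptions** (40,000 trials per case; log-SDs 0.3, 0.5, 0.8; means 90 or 150 s for three groups, 120 s for six; 5 to 80 successes per group).

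- Identical skewed, truncated distributions: ordinary ANOVA 4.5-4.9% with equal sizes, 4.7-5.0% with unequal sizes, 5.1% with six unequal groups. The level is held.
- Unequal SDs, equal sizes: 5.6-6.7%.
- Smallest group widest: 13.1-17.2% (six groups 18.6%). Smallest group narrowest: 1.7-2.4% (six groups 2.1%).
- Welch on raw seconds: 5.9-9.7% with the smallest group widest, and 5.6-10.0% for identical skewed distributions at unequal sizes. The worst case has a group of only 5.

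**Step 4: the log scale.** With the Step 2 inputs, Welch on log seconds rejects in about 7-19% of trials, including 9.2-18.7% at 40 per group. Equal arithmetic means with unequal spread imply unequal geometric means, so the log test answers a different question.

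**The case against.** A reader might infer that this ANOVA does not hold its 5% level, or that it will call routes faster too often. The documents do not support that. They never say the times are skewed or the variances unequal, and they give no SD, success rate or sample size. Inflation needs unequal spread and unequal size together, with the larger spread in the smaller group. The Background gives only a direction for success, from trained users, and nothing on spread.

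The reverse pairing is also possible: keeping only successes within 7 minutes removes slow users and could narrow the spread on a hard route. Against that, the critical-error lists suggest more steps for the atomizer (six errors besides the time limit) and intramuscular kit (five) than for the spray (two), and longer tasks often vary more. That is inference, not evidence from the plan. Moreover, if kit and instructions had no effect at all, successful times would share one distribution and the level would hold.

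The consequence is also limited. Time is secondary, and the rules for calling a route more user-friendly or preferred rest on success rates and Likert scores.

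All of this stands. It removes any claim about direction or size in this trial. It does not remove the selection problem, or the absence of any safeguard should variances differ.

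**Conclusion.** The point holds in a limited form. The planned time comparison is conditional on a post-randomisation outcome, so it is not a randomised comparison of kits. Separately, its 5% level is not guaranteed if both spread and analysed group size differ. The size is about 8-13% in one direction and about 3% in the other under the first set of assumptions; wider SD contrasts give 13-19% and about 2%. These figures rest wholly on assumed SDs, group sizes and distribution. Skew, truncation or unequal size alone leave the level near 5%. A change is worth making because it is cheap and time serves two listed secondary objectives, but the primary result is not affected.

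**What to change.** 1. Make the time comparison in all randomised participants. Keep everyone with a critical error or no administration as not successful by 7 minutes: censored at 420 s in a log-rank test, or tied at the worst rank in a rank test. This removes both the selection and the reliance on equal variances.
2. If a success-only comparison of means is kept, label it descriptive or conditional on success. Use Welch's ANOVA on raw seconds with Games-Howell pairs, and report median and IQR beside the mean.
3. Use Welch on log seconds only if the target is stated as a ratio of geometric means. It does not hold 5% for equal arithmetic means.

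The cost is SAP wording; these are standard SPSS procedures. There are two downsides. The all-randomised result mixes success with speed and is not a difference in mean seconds. Raw-seconds Welch stays somewhat above 5% when groups are small and skewed.
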